Blood sampling – Blood (~ 20 ml) will be sampled from an antecubital or hand vein for subsequent analysis of circulating factors pertinent to inclusion/exclusion criteria, including glucose, aspartate aminotransferase, alanine aminotransferase, and total bilirubin. These blood analyses will be performed in on-site (Piccolo Xpress, Abaxis, Union City, CA). Testing for Hepatitis B/C will be performed at a local, external clinical lab (e.g. University of Colorado-Health North). Per the Medical Monitor's discretion follow up blood draws maybe requested.

Visit 2: Resting Metabolic Rate (ventilated hood technique, indirect calorimetry) for 45 minutes and blood pressure will be measured. An oral glucose tolerance test will be performed.

Protocol Title:	Does Dapagliflozin Provide Additional Health Benefits To Dietary Counseling For Weight Loss? Clinical Research Protocol Title: Dapagliflozin Promotes Favorable Health Benefits That Are Independent Of Weight Loss In Overweight/Obese Adults
Protocol Type:	Biomedical
Date Submitted:	03/01/2018
Approval Period:	Draft
Important Note:	This Print View may not reflect all comments and contingencies for approval. Please check the comments section of the online protocol. Questions that appear to not have been answered may not have been required for this submission. Please see the system application for more details.

These procedures are standard for our lab. Each of the procedures is currently active in other IRB-approved protocols (e.g. 14-5201H).

Blood pressure will be determined three times using the left arm via standard procedures. Each assessment will be separated by 3 minutes. The mean of the three measurements will be recorded.

Participants will report to the laboratory early in the morning, following a 12-hour fast and 24-hour abstention from exercise. An intravenous catheter will be inserted into an antecubital or hand vein and kept patent with a saline drip. Following baseline blood sampling for fasting glucose and insulin, participants will ingest 75 g of dextrose dissolved in 250 ml of water over 10-minutes. Venous blood (~ 9 ml) will be sampled at time 0 (baseline) and 5, 10, 15, 20, 30, 45, 60, 75, 90 105 and 120 minutes for determination of concentration of blood glucose (2300 STAT Plus Glucose Lactate Analyzer, YSI Inc., Yellow Springs, Ohio), and insulin (commercially available assay).

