Prior to the start of the oral glucose tolerance test, venous blood (~ 20 ml) will be sampled, and plasma/serum and red cells isolated and stored at -70°C for subsequent analysis of circulating markers of inflammation (High sensitive C-Reactive Protein, Tumor Necrosis Factor Alpha, and Interleukin 6) and oxidative stress (oxidized low density lipoprotein concentration, and thiobarbituric acid reactive substances).

Visit 3: Appetite and hunger will be assessed.

These procedures are standard for our lab. Each of the procedures is currently active in other IRB-approved protocols (e.g. 12-3567H).

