On a day different to the oral glucose tolerance day, participants will report to the laboratory early in the morning, following a 12-hour fast and 24-hour abstention from exercise. An intravenous catheter will be inserted into an antecubital or hand vein and kept patent with a saline drip. Participants will be provided with a standardized "priming meal" comprising a commercially available, mixed-nutrient liquid meal, dosed to 1 kcal per kg body mass (Ensure, Ross Laboratories, Abbott Park, IL; 64% CHO, 22% fat, 14% protein). One hour following consumption of this priming meal, participants will be presented with a pre-weighed buffet of food from which they will have opportunity to eat ad libitum quantities over a 30 minute period. The remaining uneaten food will be reweighed and participants' energy and macronutrient intakes will later be determined using the Food Intake Analysis System software (U Texas Health Sciences Center, Houston). Prior to the standardized primer meal, and to the buffet, and then every 60 minutes over 3 hours following the buffet, participants will be asked to rate their perceptions of hunger and satiety using a visual analog scale. At these same time points, venous blood (~ 20 ml) will be sampled, and plasma/serum isolated and stored at -70°C for subsequent determination of concentrations of hunger and satiety hormones (e.g. ghrelin, peptide YY, leptin, and insulin). At the conclusion of these tests, the study participant will give a form in which to record the amounts of food and beverage (except water) they eat and drink for three consecutive days, including 2 week days and 1 weekend day. Upon completion of the food records, the form will be returned to the research team. This information will be used to establish baseline dietary intake and will be useful information for the nutrition counselors seeking to help the participants lose weight.

Protocol Title: Does Dapagliflozin Provide Additional Health Benefits To Dietary Counseling For Weight Loss?
Clinical Research Protocol Title: Dapagliflozin Promotes Favorable Health Benefits That Are Independent Of Weight Loss In Overweight/Obese Adults

Protocol Type: Biomedical

Date Submitted: 03/01/2018

Approval Period: Draft

Important Note: This Print View may not reflect all comments and contingencies for approval. Please check the comments section of the online protocol.
Questions that appear to not have been answered may not have been required for this submission.

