Please see the system application for more details.

Visits 4-27: During the first 6 weeks participants will meet with a study counselor 2 times per week for dietary counseling and measurement of body weight. During the second 6-week period they will meet 1-2 times per week for dietary counseling and body weight measurement, depending on whether or not they are meeting weight loss goals. If they are losing weight as prescribed, they will meet only once per week, but if they are not meeting weight loss goals they will meet 2 times per week. Participants will need to fast for 10 hours prior to the weigh-in. On 2 random counseling occasions between weeks 4 and 10, they will be asked to recall what they ate during the previous 24 hours. If participants fail to achieve their target body weight (within 1 kg or 2.2 lbs) on three consecutive weighing sessions, they will be provided with additional counseling and instructions to aid in achieving your target body weight.

During the first two weeks of the 12 week intervention, participants will ingest one pill daily (5 mg DAPA) and for the remaining 10 weeks participants will ingest 2 pills daily (a total of 10 mg DAPA). On 3 random weigh-in occasions between weeks 4 and 10, participants will be asked to recall what they ate during the previous 24 hours.

Visit 28: Resting Metabolic Rate Test, Oral Glucose Tolerance Test, and Blood Pressure will be measured (e.g. the final week of daily ingestion of Dapagliflozin). See description of Visit 2.

Visit 29: in the HPCRL appetite and hunger will be assessed this visit will occur in week 12 (e.g. during the final week of daily ingestion of Dapagliflozin). Body composition will be measured at this visit or early the following week (e.g. week 13). The study participants will also be given the 3-day food intake record form to be completed and returned to the research team.

b) Explain why human subjects must be used for this project.

Dapagliflozin is approved for human use. Due to potential species differences it would not be appropriate to perform these studies on experimental animals.

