Baseline (pre-counselling) differences between placebo and SGLT2 inhibition groups were compared using independent Student t-Tests. Consistent with the experimental design (randomized, double-blind, parallel, repeated measures) the influence of SGLT2 inhibition on the physiological responses to dietary counselling was examined using two-way (group: placebo vs. SGLT2 inhibition x time: before vs. after dietary counselling) analysis of variance (ANOVA). The influence of SGLT2 inhibition and dietary counselling on the dynamic responses to oral glucose ingestion were examined using three-way ANOVA (placebo vs. SGLT2 inhibition x before vs. after dietary counselling x time points during the OGTT). Pairwise multiple comparison procedures were performed using the Holm-Sidak Method. Relations of interest were described using Pearson product-moment correlations. The level of statistical significance was set at $P<0.05$. Data are reported as mean and standard deviation, unless otherwise indicated. Calculations were performed using commercially available statistical software (SigmaStat 3.0, Systat Software Inc., San Jose, California, USA).

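### Five fasting markers rest on one draw per period, and two fasting insulin values are never combined: a modest, recoverable loss of precision

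*Combined protocol and SAP*

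**What the plan says.** Section 2(a), Study Procedures, describes Visit 2 as an early-morning visit with standard preparation: "Participants will report to the laboratory early in the morning, following a 12-hour fast and 24-hour abstention from exercise". Before the glucose load, "Prior to the start of the oral glucose tolerance test, venous blood (~ 20 ml) will be sampled, and plasma/serum and red cells isolated", for later analysis of "circulating markers of inflammation (High sensitive C-Reactive Protein, Tumor Necrosis Factor Alpha, and Interleukin 6) and oxidative stress" (oxidised LDL and TBARS). The OGTT itself starts with its own fasting values: "Following baseline blood sampling for fasting glucose and insulin". After treatment, "Visit 28: Resting Metabolic Rate Test, Oral Glucose Tolerance Test, and Blood Pressure will be measured", with a reference back to the Visit 2 description, so the marker draw is repeated once.

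Visit 3, the appetite test, is a separate occasion: "On a day different to the oral glucose tolerance day, participants will report to the laboratory early in the morning, following a 12-hour fast", again with 24 hours without exercise. Hunger ratings are taken before the priming meal, before the buffet and hourly afterwards. "At these same time points, venous blood (~ 20 ml) will be sampled, and plasma/serum isolated and stored at -70°C", for appetite hormones that include insulin. The first of these samples is fasting. Visit 29 repeats the appetite assessment in week 12 but, unlike Visit 28, carries no reference back to the earlier description.

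The SAP analyses responses to counselling by "two-way (group: placebo vs. SGLT2 inhibition x time: before vs. after dietary counselling) analysis of variance (ANOVA"). It names no endpoints, gives no rule for replicate values, and analyses the OGTT curve separately by three-way ANOVA.

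**The concern.** Reduced inflammation and oxidative stress are among the non-weight benefits on which the rationale rests (sections 1(a) and 3(a)), so the first aim depends partly on these markers. Each enters the analysis as one value before and one after. Day-to-day variation in a person's fasting level therefore enters every change score twice, undiluted. A second fasting sample, taken on another day under the same conditions, is already in the freezer.

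For insulin the second value is not merely available but planned. With two fasting values per period and no rule, precision is lost and the analyst can choose between them after seeing the data.

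Precision is scarce. The IRB letter aims for 60 completers, and enrolment was raised to 200 to reach that number. The documents contain no power calculation.

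**Working it through.** **Inputs from the documents.** 60 completers (IRB approval letter); significance level 0.05 (SAP); one marker draw per period (section 2(a), Visits 2 and 28); a second fasting draw at Visit 3, inferred at Visit 29.

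**Assumptions.** 1:1 allocation, so 30 per arm, and a two-sided test; neither is stated. Let w be the day-to-day variance of a fasting value and c the variance of true individual change. The documents give neither, so a range is used. There is no sample-size figure in the plan to reproduce.

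**Reference point.** With two groups and two times, the group-by-time test is a two-sample t-test on change scores. With 30 per arm (58 degrees of freedom), the noncentral t distribution gives 80% power at a difference of 0.74 SD of change and 50% power at 0.51 SD.

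**Formulas.**
- One day per period: Var(change) = c + 2w.
- Mean of two independent days per period: Var(change) = c + 2(w/2) = c + w.
- SE ratio = √[(c + w)/(c + 2w)]; sample-size equivalent = (c + 2w)/(c + w).

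Example, w/c = 0.25: (1 + 0.25)/(1 + 0.50) = 0.833; √0.833 = 0.913, a 9% fall; 1/0.833 = 1.20.

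| Assumed w/c | Variance ratio | SE falls by | Acts like N times | Power, from 50% |
|---|---|---|---|---|
| 0.1 | 1.1/1.2 = 0.917 | 4% | 1.09 | 53% |
| 0.25 | 1.25/1.5 = 0.833 | 9% | 1.20 | 57% |
| 1 | 2/3 = 0.667 | 18% | 1.50 | 67% |
| 2 | 3/5 = 0.600 | 23% | 1.67 | 72% |
| c = 0 (limit) | 0.500 | 29% | 2.00 | 79% |

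**Correlated days.** If the two day errors within a period correlate at ρ, then Var(change) = c + (1 + ρ)w. At an assumed ρ = 0.5:
- w/c = 0.1: 1.15/1.2 = 0.958, SE falls 2%.
- w/c = 0.25: 1.375/1.5 = 0.917, SE falls 4%.
- w/c = 1: 2.5/3 = 0.833, SE falls 9%.
- w/c = 2: 4/5 = 0.800, SE falls 11%.
- c = 0: 0.750, SE falls 13%.

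For any given w/c, the independent-days figure is therefore an upper bound. With days of equal variance, averaging cannot increase the variance.

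**Assay count.** 60 completers × 2 periods × 5 markers = 600, or 120 per marker.

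**The case against.** The strongest reply is that nothing in the plan is wrong. One standardised fasting draw before and one after gives an unbiased group-by-time comparison, and almost any trial could reduce noise by assaying more. That stands, and it limits the point to efficiency.

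The size of the gain is also assumption throughout. If slow drift or varied individual response dominates, the gain approaches zero. The c = 0 limit requires everyone to change by the same true amount, which is implausible when the protocol itself provides for people who miss weight targets. The interval between Visits 2 and 3 is not stated, and one infection could affect both samples.

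Several practical objections also stand and narrow the remedy:
- Visit 2 insulin is time 0 of the OGTT curve; replacing it with a two-day mean would break the within-test series.
- The documents do not say that both insulin values come from the same assay.
- The Visit 29 draw is inferred.
- Visit 3 plasma is earmarked for appetite hormones, spare volume is not documented, and red cells are isolated only at Visit 2.
- Participants carried over from 14-5531H do not repeat the OGTT (section 8(a)), so their Visit 2 values may be considerably older.

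A reader might infer that every fasting marker rests on a single draw. That is not so for insulin. A reader might also want blood pressure added at Visits 3 and 29. It is already the mean of three readings on the day, and extra sessions would be new data collection rather than use of samples in hand.

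Finally, the sponsor's protocol is listed as an attachment but is not among the documents, so the absence of a combining rule is established only for the text available.

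**Conclusion.** The point holds as a loss of efficiency. The five markers are planned from one fasting draw per period, and no rule combines the two fasting insulin values. Under assumed w/c of 0.1 to 2 with independent days, averaging would lower the standard error by about 4% to 23%, equivalent to 1.09 to 1.67 times the participants; at ρ = 0.5 the same range gives about 2% to 11%. It would be tempting to say that averaging doubles the effective sample. That is the theoretical ceiling (29%), and the documents give no support for reaching it. Nor do they support reading the single draw as a source of bias.

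The insulin part is the firmer one, because both values are already planned and a rule also removes an open analytic choice. It assumes that fasting insulin is a stand-alone endpoint in the two-way ANOVA, which the SAP does not state. The marker part depends on sample volume and matrix.

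**What to change.** Before unblinding, add to the SAP:

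1. For stand-alone fasting insulin in the two-way ANOVA, the before value is the mean of the Visit 2 and Visit 3 fasting values, and the after value is the mean of Visits 28 and 29. If one is missing, use the other.
2. Confirm that the same insulin assay is used on both days, and state in the protocol that the fasting pre-meal draw is taken at Visit 29.
3. Keep OGTT time 0 unchanged in the three-way ANOVA.
4. For participants carried over from 14-5531H whose Visit 2 data come from that study, do not average across days; use the value closest to the start of treatment.
5. Where the volume and matrix of the stored pre-meal plasma or serum allow, assay those aliquots for hs-CRP, TNF-alpha, IL-6, oxidised LDL and TBARS, and average by the same rules.

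Items 1 to 4 cost only text and a check with the laboratory. Item 5 costs up to about 600 assays and uses stored sample, but needs no extra visit, needle or participant.

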2. Weight loss associated with dietary counseling and the use of Dapagliflozin (SGLT2 inhibition) is characterized by normal circulating satiety signals rather than the usual diet-induced changes in circulating peptides that increase hunger and reduce satiety.

c) Proposed Start Date (may not precede IRB approval date):

On receipt of IRB approval.

2.

Study Procedures (If this is a student project, the methods section of the thesis or dissertation proposal must be attached in section #16 - Attachment section.)

a) In lay language, describe all the procedures, from screening through end-of-study, that the human subject must undergo in the research project, including study visits, drug treatments, randomization and the procedures that are part of standard of care. Please note: Do NOT respond "See Attachment Section." If you would like to add tables, charts, etc., attach those files in the Attachment section (#16).

OVERVIEW

This is a randomized, prospective, placebo-controlled, double blind, repeated measures study. 60 overweight/obese adults (body mass index > 27.5 kg/m²) will be recruited for participation and randomly assigned to one of two 12 week treatments: (1) daily oral administration of Dapagliflozin with dietary counseling to promote weight loss; or, (2) daily oral administration of a placebo with dietary counseling to promote weight loss.

Study participants will report to the research facilities on the Colorado State University main campus on 29 separate occasions:

Visit 1: study participants will undergo screening: medical history, 12-lead electrocardiogram and blood pressure assessment at rest and during incremental exercise to volitional exhaustion, blood sampling, and measurement of body composition.

Visit 2: an oral glucose tolerance test will be performed and resting metabolic rate and blood pressure will

Protocol Title: Does Dapagliflozin Provide Additional Health Benefits To Dietary Counseling For Weight Loss?
Clinical Research Protocol Title: Dapagliflozin Promotes Favorable Health Benefits That Are Independent Of Weight Loss In Overweight/Obese Adults

Protocol Type: Biomedical

Date Submitted: 03/01/2018

Approval Period: Draft

Important Note: This Print View may not reflect all comments and contingencies for approval. Please check the comments section of the online protocol.
Questions that appear to not have been answered may not have been required for this submission.
Please see the system application for more details.

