be measured.

Visit 3: appetite and hunger will be assessed and participants will be given a 3-dietary record form to complete.

Visits 4-27: 12 weeks of nutrition counseling/weighing (upto 2 visits per week for 12 weeks). Concurrent with these visits, research participants will ingest, on a daily basis, either Dapagliflozin or placebo.

Visit 28: an oral glucose tolerance test will be performed and resting metabolic rate and blood pressure will be measured.

Visit 29: appetite and hunger will be assessed; body composition will be measured, and participants will be given a 3-day dietary record form to complete.

DETAILED DESCRIPTION OF STUDY PROCEDURES

Visit 1: study participants will provide informed consent and undergo screening: medical history, 12-lead electrocardiogram and blood pressure assessment at rest and during incremental exercise to volitional exhaustion, blood sampling, and measurement of body composition.

These screening procedures are standard for our lab. Each of the procedures is currently active in other IRB-approved protocols (e.g. 12-3767H, 08-611H, 14-4756H).

Health History - Potential participants will complete a standardized health history questionnaire that will address past and present medication use, allergies, past and present medical conditions and physical injuries, and habitual use of alcohol and tobacco.

Body composition - Percent body-fat, fat-free mass, total and regional adipose tissue mass, and total bone mineral density will be determined using a whole-body dual energy x-ray absorptiometry scan (DEXA, Model DPX-IQ Lunar Corp., Madison, WI).

Maximal graded exercise stress testing - A 12-lead ECG, arterial blood pressure (brachial sphygmomanometer) will be obtained during quiet resting conditions in the supine and upright sitting positions, and during incremental stationary cycle ergometer or treadmill exercise until volitional fatigue. During exercise, oxygen consumption, carbon dioxide production and ventilation may be determined by indirect calorimetry. All data from these tests will be reviewed by a cardiologist. Only those subjects demonstrating no signs or symptoms of disease will be invited to participate in the study.

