*** Radioisotopes or Radiation Machines ***

You selected NO for Radioisotopes in the General Checklist. If you would like to add Radioisotopes, change the selection to YES in general Checklist.

4.

Radioisotopes or Radiation Machines Please note: For projects requiring radiation procedures, please contact the CSU Radiation Control Office (RCO). For more information see:
<http://www.ehs.colostate.edu/WRad/Home.aspx> :

a) If applicable, summarize in lay language the radiographic diagnostic and therapeutic procedures associated with this protocol.

Body composition will be measured by dual energy x-ray absorptiometry (DEXA) at pre and post treatment

b)

Are the radiation procedures being performed a normal part of the clinical management for the medical condition that is under study (Standard of Care) or are the procedures being performed because the research subject is participating in this project (extra CT scans, more fluoroscopy time, additional Nuclear

Protocol Title: Does Dapagliflozin Provide Additional Health Benefits To Dietary Counseling For Weight Loss?
Clinical Research Protocol Title: Dapagliflozin Promotes Favorable Health Benefits That Are Independent Of Weight Loss In Overweight/Obese Adults

Protocol Type: Biomedical

Date Submitted: 03/01/2018

Approval Period: Draft

Important Note: This Print View may not reflect all comments and contingencies for approval. Please check the comments section of the online protocol.
Questions that appear to not have been answered may not have been required for this submission.
Please see the system application for more details.

Medicine Studies, etc.,) (Not Standard of Care)? If some procedures are Standard of Care and some are Not Standard of Care, check both boxes.

NOT STANDARD OF CARE

If it is not standard of care, complete the rest of this section. Provide the CSU RCO approval information

X STANDARD OF CARE

If it is only standard of care, skip the rest of this section.

CSU Radiation Control Office approved protocol number:

CSU Radiation Control Office protocol approval date:

For more information, see the RCO website at: <http://www.ehs.colostate.edu/Wrad/home.aspx> or Contact: [name], Radiation Safety Officer, at [contact].

*** * * Medical Equipment for Human Subjects and Laboratory Animals; Investigational Devices * * *****5. Medical Equipment for Human Subjects**

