***** Drugs, Reagents, or Chemicals *******7. Drugs, Reagents, or Chemicals**

- a) Please list in the space below all investigational drugs, reagents or chemicals to be administered to subjects during this study.
- b) Please list in the space below all commercial drugs, reagents or chemicals to be administered to subjects during this study.

Drug Name	Dapagliflozin
Source (e.g., Pharmacy, Sponsor, etc.,)	AstraZeneca Pharmaceuticals LP
If not premixed, where will the material be mixed and by whom	Pre-mixed by Bristol-Myers Squibb Company
Manufacturer	Bristol-Myers Squibb Company
IND # (if available)	n/a
Dosage	5 mg/day of Dapagliflozin for the first 14-days, and then a dose increase to 10 mg/day of Dapagliflozin for remaining 10 weeks.
Administration Route	Oral
Y	Are these new or different uses of these commercially available drugs, reagents, or chemicals?
N	IND Regulations

Please read the IND Statements

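### The final DEXA may fall in week 13, after the planned 84 days of drug, and the SAP pools week-12 and week-13 scans without a window or a record of the gap.

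*Combined protocol and SAP*

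**What the plan says.** **Length of treatment.** Participants are "randomly assigned to one of two 12 week treatments" (Purpose, Study Procedures, Background, item 2(a), overview). The dosage entry in Drugs, Reagents, or Chemicals, item 7(b), reads "5 mg/day of Dapagliflozin for the first 14-days, and then a dose increase to 10 mg/day of Dapagliflozin for remaining 10 weeks". Counseling has the same length: "12 weeks of nutrition counseling/weighing (upto 2 visits per week for 12 weeks".

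**Timing of the final DEXA.** Three places describe it, and they differ:

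- Item 2(a), overview: "Visit 29: appetite and hunger will be assessed; body composition will be measured". No later date is offered.
- Item 2(a), detailed description of Visit 29: the appetite assessment comes first, and "this visit will occur in week 12 (e.g. during the final week of daily ingestion of Dapagliflozin". The next sentence reads "Body composition will be measured at this visit or early the following week (e.g. week 13".
- Radioisotopes or Radiation Machines, item 4(a): "Body composition will be measured by dual energy x-ray absorptiometry (DEXA) at pre and post treatment". Post treatment is not defined.

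**Other final measurements.** The detailed text places metabolic rate, glucose tolerance and blood pressure (Visit 28) and appetite (Visit 29) in the last week of ingestion.

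**Analysis.** The SAP examines the physiological responses with a two-way ANOVA: group by a single time factor with two levels, before and after counseling. It gives no visit window, timing covariate or sensitivity analysis. Nothing in the protocol asks for the interval from last pill to scan to be recorded.

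**The concern.** DEXA is the only final laboratory measurement that the text allows to fall outside the last week of pills. If some active-arm participants are scanned on drug and others after it has stopped, their results are averaged into one post-treatment value with nothing in the data set to separate them.

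Stopping placebo has no pharmacological effect. Stopping the drug ends whatever urinary glucose and fluid loss it was causing. DEXA fat-free mass includes body water, so any water that returned would raise active-arm fat-free mass and lower percent fat with no change in fat.

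The trial asks whether benefits go beyond those of weight loss, so body composition is relevant to interpretation. The SAP also plans correlations. Some could pair on-drug physiology from week 12 with off-drug body composition from week 13 in the same person.

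**Working it through.** The documents give no effect size, SD or power for body composition, so there is no stated figure to reproduce. The check is a timeline followed by an illustration of what would determine the size.

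**1. Timeline (dosage entry, item 7(b)).** 14 + 10 × 7 = 84 days, and 84 / 7 = 12.0 weeks. Week 13 is days 85 to 91. A week-13 scan therefore falls after the planned last dose and after the planned 12 weeks of counseling.

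**2. The three statements side by side.** The overview allows week 12 only. The detailed text allows week 12 or early week 13. The radiation section fits a scan after the last dose but gives no date. They cannot all be followed as one rule.

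**3. What differs between arms.** The window is not arm-specific and the trial is double-blind, so the share of scans in week 13 should be similar in both arms. The end of counseling is also common to both. Only drug withdrawal is specific to the active arm, and equal timing does not cancel it.

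**4. How the size would scale.** Let q be the share of active-arm scans done off drug and w the mean water regained by then (kg).

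- Shift in the fat-free-mass contrast = q × w.
- Added active-arm variance = q(1 − q)w².

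Neither q nor w is in the documents. Purely as assumptions, take q from 0.25 to 0.75 and w from 0.5 to 1.5 kg:

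- lowest: 0.25 × 0.5 = 0.125 kg
- middle: 0.50 × 1.0 = 0.50 kg
- highest: 0.75 × 1.5 = 1.125 kg

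For scale, assume an SD of change of 1.5 kg and 30 per arm (60 studied, equal allocation assumed). The 95% CI half-width is then 2.00 × 1.5 × √(2/30), about 0.78 kg. Added variance at the middle values is 0.5 × 0.5 × 1.0² = 0.25 kg², against 1.5² = 2.25 kg², or 11%.

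**5. Direction.** Assume 95 kg body mass with 35 kg fat. Percent fat is 35/95 = 36.8%. After 1 kg of water returns it is 35/96 = 36.5%. A drug effect on fat-free mass through fluid would shrink, while an apparent percent-fat benefit could grow slightly.

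The assumed range runs from trivial to larger than the assumed precision. That shows the size is undetermined; it does not show that it is large.

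**The case against.** **The mechanism has little support in the documents.** Increased urination appears under Risks only within a list of reactions reported in more than 2% but less than 8.5% of patients. Dehydration appears as an exclusion criterion. The urinary glucose figures of 45 to 80 g/day (180 to 320 kcal/day) are cited for patients, whereas known type 2 diabetes is excluded here. The Background reports negligible weight loss with these drugs in adults with healthy glucose control, which sits badly with a large general fluid deficit. The documents do not say how fast the effect ends, and early week 13 may be only a day or so after the last pill. All of this stands, and it is why no size can be claimed.

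**A reader might infer that the mixing affects the active arm alone, or that it biases in a known direction.** The documents do not support this. The window and the end of counseling apply to both arms, and blinding should balance scan timing. What remains is that withdrawal itself acts in one arm, with an effect that may differ in sign between fat-free mass and percent fat.

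**A reader might also try to size the effect from energy:** 7 days at 180 to 320 kcal is 1,260 to 2,240 kcal, and 7/84 = 8.3% of the course. This fails. Someone dosed for 84 days has had the whole planned course by week 13, and the comparison needs a 91-day course that nobody planned. A week-12 scan may even come before the last few pills.

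**Off-drug scanning is permitted, not shown.** No section gives the day of the last pill relative to the scan. The attachments list deviations on an extended intervention period and on its duration, by title only, so actual dosing periods varied. This stands, and it is a reason to record the interval.

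**Moving DEXA to Visit 29 could bring its own artefact.** If that visit follows the Visit 3 procedure, it includes a saline drip, a liquid meal and a buffet. This is fair, and the fix has to specify the order.

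**Conclusion.** The inconsistency is real. The detailed text permits a final DEXA on day 85 or later, the overview does not, and the SAP would analyze both timings as one value. Off-drug scans may shift or dilute the drug contrast in fat-free mass and percent fat and add noise that depends on scanner booking.

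The size cannot be estimated from the documents and may be small. The kilogram figures above rest entirely on assumed q, w and SD. The timeline rests on the planned 84 days, and actual durations may differ. The documents name no primary endpoint, and body weight is measured separately at the counseling visits. The point is therefore one to consider, not a threat to the trial's main conclusions.

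**What to change.** 1. Reconcile the overview, the detailed Visit 29 text and the radiation section so that they give one time for the final DEXA: in week 12, either at Visit 29 before the liquid meal and buffet, or on another week-12 day while pills are still being taken. This changes when a measurement is made and leaves dosing as planned.
2. Record days from last pill to scan for every participant in both arms.
3. For scans already taken in week 13, keep them in the main analysis and repeat the body-composition analysis without them as a sensitivity analysis. Report how many such scans there were in each arm.

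**Cost.** Tighter scanner booking around a visit that already takes place, one extra data item, and one sensitivity analysis on a somewhat smaller sample. The Event History shows the protocol expired in March 2019 and the SAP is written in the past tense. If data collection is complete, step 1 can no longer change conduct. Step 2 then means recovering the interval from dispensing and scan dates where these were kept, and step 3 carries the remedy.
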